9. IFTA
10. IFTA and Inflammation (IFTA and ci $>$ 0)
11. Acute and chronic forms of ABMR
12. eGFR at various thresholds (less than 30, 40, 50 mL/min/1.73 m² at one year; and a five-point decline from Day 30 to Day 365)
13. Graft loss
14. Mortality

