5.3.12 Acute Rejection

For study purposes, diagnoses of rejection require biopsy confirmation. Both acute TCMR and ABMR (acute and chronic) will be assessed and graded according to published criteria [Solez et al, 2008].

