6.1.2 Secondary Efficacy Endpoints

Comparisons between treatment groups regarding incidence will rely upon assessments for the following results:

- De novo DSA formation over the course of 1 year
 - De novo DSA (positive / negative / indeterminate) up to Day 365
 - Class I and Class II DSA will be assessed by a central HLA lab at 1, 3, 6, 9, and 12 months. Overall, Class I and Class II DSA occurrence (positive / negative) of

the period from transplant to Month 12 will be assessed based on assessments at each visit.

- Endpoints for the subset of DSA positive subjects:
 - initial MFI values and antibody strength (mild, moderate, strong) based on MFI
 - post-transplant peak MFI and antibody strength
 - DSA persistent (yes/no) will be assessed by sponsor based on DSA lab data
 - C1q-binding DSA (positive/negative)
 - DSA IgG3 isotype (positive/negative)

For de novo DSA positive subjects, their initial MFI values and antibody strength, peak MFI and antibody strength, and DSA persistence (yes/no) will be assessed by sponsor based on DSA lab data.

- IA
 - Immune Activation (IA) from Day 1 to Day 365 visit
 - Immune Activation (IA) during the period from Day 30 to Day 365 visit

IA will be regarded as persistent if IA is detected for positivity for any two measurements on or before Day 365 visit.

- TG during the first year

The presence of TG will be reported where TG is defined as $cg > 0$ on centrally-interpreted institutional protocol biopsy or biopsy obtained for cause during the first year post-transplant with +2 months visit window.

- Microcirculatory Inflammation during the first year

The presence of microcirculatory inflammation will be reported where microcirculatory inflammation is defined as $g + ptc \geq 2$ on centrally-interpreted institutional protocol biopsy or biopsy obtained for cause during the first year post-transplant, with +2 months visit window.

- IFTA and Inflammation during the first year

The presence of IFTA and inflammation will be reported where IFTA and inflammation is defined as IFTA positive and inflammation positive ($i > 0$) on centrally-interpreted institutional protocol biopsy or biopsy obtained for cause during the first year post-transplant, with +2 months visit window.

- Thresholds for eGFR

- Values less than 30, 40, and 50 mL/min/1.73 m²

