These threshold endpoints will be calculated for months 1, 3, 6, 9, and 12 using the Modification of Diet in Renal Disease (four variable-MDRD) criteria. Assessments are positive or negative.

- Five-point decline in eGFR

The decline in eGFR will be calculated with respect to the eGFR value at Day 30 visit.

- Traditional transplantation composite endpoint

Incidence will be assessed at month 12 for the following:

- Graft loss (defined as retransplantation, transplant nephrectomy, or a return to dialysis for at least a six week duration, or subject death)
- Death
- BPAR – positivity will be determined by local biopsy, central pathology, or reported adverse events.
- Composite occurrence of either graft loss, death, BPAR, and loss-to-follow-up

- Histopathology grading within 1 year

Central histopathology grading over 1 year will be diagnosed according to the BANFF diagnostic categories and subcategories that include the following:

- Normal
- Antibody mediated changes
 - C4d deposition without morphologic evidence of active rejection
 - Acute ABMR (grades: I, II, and III)
 - Chronic active ABMR
 - ABMR: either Acute ABMR or Chronic Active ABMR
- Borderline changes
- TCMR
 - Acute TCMR (grades: IA, IB, IIA, IIB, and III)
 - Chronic active TCMR
- IFTA (grades: I, II, and III)
- Other: all categorical findings will be summarized.
- In addition to the categories above, specimens will be given individual scores for the following: glomerulitis (g), tubulitis (t), intimal arteritis (v), mononuclear cell interstitial inflammation (i), early allograft Glomerulopathy (cg), tubular atrophy (ct), interstitial fibrosis (ci), vascular fibrous intimal thickening (cv), arteriolar hyaline thickening (ah), peritubular capillaries (ptc) and mesangial matrix (mm).

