7 STATISTICAL METHODOLOGY

7.1 General Considerations

All numeric and categorical efficacy and safety endpoints will be descriptively summarized. For continuous variables, descriptive statistics will include the number of subjects (n), mean,

standard deviation, median, minimum and maximum. Frequencies and percentages will be displayed for categorical data.

Summaries based on the FAS, mFAS, PPS, and BAS (e.g. disposition, baseline and efficacy data) will be presented by planned treatment group, unless specifically stated otherwise. Unless otherwise stated, all analyses will be performed using data pooled across sites. Subject listings of all data from the CRFs as well as any derived variables will be presented.

All statistical comparisons will be made using two sided tests at the $\alpha = 0.05$ significance level unless specifically stated otherwise. All null hypotheses will be of no treatment difference, all alternative hypotheses will be two-sided, unless specifically stated otherwise. P-values will not be adjusted for multiple comparisons. In the event that any analysis set sample size falls below 15 in any treatment group, descriptive statistics will exclusively be reported with no p-values or statistical inferences. In addition, logistic regression analysis and other regression model analysis as planned in the following sections will not be performed for outcome variables that have an event rate of less than 10% (i.e. reported by fewer than 57 subjects).

Unless otherwise specified, all data processing, summarization, and analyses will be performed using SAS[®] Version 9.4 or higher.

A hard database lock will occur prior to the final analysis.

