Following secondary endpoints will be summarized with frequencies and percentages by treatment group. The incidence of events will be analyzed for treatment group differences. Analysis of treatment group differences will be implemented from logistic regression model with the same covariates of primary efficacy analysis.

1. De novo DSA formation
2. IA
3. C1q-binding DSA
4. DSA IgG₃ isotype
5. Persistence of DSA
6. Persistence of IA
7. TG (cg $>$ 0)
8. Microcirculatory Inflammation (g+ptc $>$ 2)

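### SAP 7.4.2 defines two secondary biopsy endpoints differently from SAP 6.1.2, and BPAR has several unreconciled sources

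*SAP*

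**What the plan says.** **IFTA and inflammation.** In SAP 6.1.2, "IFTA and inflammation is defined as IFTA positive and inflammation positive ($i > 0"), read centrally. The endpoint list in SAP 7.4.2 has, as item 10, "IFTA and Inflammation (IFTA and ci $>$ 0"). The score key in SAP 6.1.2 reads "mononuclear cell interstitial inflammation (i), early allograft Glomerulopathy (cg), tubular atrophy (ct), interstitial fibrosis (ci").

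**Microcirculatory inflammation.** In SAP 6.1.2, "microcirculatory inflammation is defined as $g + ptc \geq 2$ on centrally-interpreted institutional protocol biopsy" or for-cause biopsy. Item 8 of SAP 7.4.2 has "Microcirculatory Inflammation (g+ptc $>$ 2"). The protocol does not define this endpoint.

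**Rule for fitting models.** SAP 7.1 rules out regression for "outcome variables that have an event rate of less than 10% (i.e. reported by fewer than 57 subjects").

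**BPAR.** SAP 6.1.2 says "positivity will be determined by local biopsy, central pathology, or reported adverse events". Protocol 5.3.12 says "For study purposes, diagnoses of rejection require biopsy confirmation", and Protocol 2.2.1 asks for local biopsy support when rejection is suspected. Protocol 7.4.2 specifies locally read BPAR in the four-part composite (item 13) but plain BPAR in item 12. SAP 7.4.2 names BPAR among the eight risk-factor outcomes and then says that the biopsy data come from central pathology. Under SAP 3.2, one biopsy per participant goes to central grading: the one nearest month 12.

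**The concern.** The bracketed conditions in SAP 7.4.2 are what a programmer would code for the treatment comparisons. Two programmers working from different sections of the same SAP would produce different tables.

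Item 10 is the more serious mismatch, because the variable itself differs. An endpoint labelled as inflammation would be scored on fibrosis, so its result would tell the reader little beyond item 9. Item 8 differs only in the cut-off, but the cut-off can also decide whether a comparison is modelled at all.

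Both endpoints are used elsewhere. IFTA and inflammation is a risk-factor outcome (SAP 3.1.2 and 7.4.2), and microcirculatory inflammation defines a subgroup for the tacrolimus variability summaries (SAP 7.3.3).

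BPAR is a separate problem. It is item 15, a component of item 16, a risk-factor outcome and a subgroup in SAP 7.3.3, and its source changes who counts as an event. If definitions are chosen after results are seen, the choice is open to criticism as data-driven.

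**Working it through.** This is mainly a comparison of definitions. The plan gives no figure to reproduce.

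**Item 10**

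| Central biopsy | SAP 6.1.2 (IFTA and i > 0) | SAP 7.4.2 (IFTA and ci > 0) |
|---|---|---|
| IFTA, ci > 0, i > 0 | positive | positive |
| IFTA, ci > 0, i = 0 | negative | positive |
| IFTA, ci = 0, i > 0 (if it occurs) | positive | negative |
| No IFTA | negative | negative |

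Because ci scores the fibrosis part of IFTA, the ci condition removes few IFTA-positive subjects. Item 10 therefore largely repeats item 9. Protocol 5.3.7 treats a score above 0 as positive for that feature, which fits i > 0 as the marker of inflammation.

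**Item 8**

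The two rules differ only where g+ptc = 2, that is, for (g, ptc) = (0,2), (1,1) and (2,0). Assuming that each score runs from 0 to 3 (the documents do not give the range), there are 4 × 4 = 16 score pairs. Three of them sum to 0 or 1, so 16 − 3 = 13 meet the 2-or-more rule. Removing the three that sum to exactly 2 leaves 13 − 3 = 10 that meet the above-2 rule. These are counts of score pairs, not proportions of patients.

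Let k be the number of subjects scoring exactly 2:

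- count(above 2) = count(2 or more) − k.
- By the SAP 7.1 count, a model is fitted only if the count is at least 57.
- It is fitted under 2-or-more and dropped under above-2 when count(2 or more) ≥ 57 and count(2 or more) − k ≤ 56.
- That is 57 ≤ count(2 or more) ≤ 56 + k.
- With k = 10, as illustration only, the interval is 57 to 66.

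The count of 57 is 10% of 57/0.10 = 570 subjects; 10% of the planned 550 is 55. Items 8 and 10 are analysed in the Biopsy Analysis Set (SAP 5.5 and 7.4), whose size is not given. If the 10% rate is applied within that set, the threshold is some smaller number T and the interval becomes T to T − 1 + k. It moves but keeps its width of k.

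**BPAR**

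| Case | SAP 6.1.2 as worded | Protocol 5.3.12 | SAP 7.4.2 central-pathology sentence, if it covers BPAR |
|---|---|---|---|
| Rejection on the centrally graded biopsy | counts | counts | counts |
| Rejection on another biopsy, read locally | counts | counts | does not count |
| Rejection reported only as an adverse event | counts | does not count | does not count |

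The source also affects the data window and the analysis set. SAP 7.10.3 uses central pathology to Day 426 but most other endpoints to Day 386. SAP 7.4 uses the Biopsy Analysis Set for central pathology findings and the mFAS otherwise. No rule is given for sources that disagree. The SAP revision history lists no change to any of these three definitions.

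**The case against.** The strongest reply is that these are drafting slips. SAP 6.1.2 is the definitional section, 7.4.2 gives bracketed shorthand, the i score is tested on its own anyway, and the trial is labelled exploratory with unadjusted p-values. That limits the severity but does not remove the conflict, because no rule says which section governs.

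For item 8, a lost bar under the sign in PDF text cannot be wholly excluded. Comparison signs with the bar survive in 6.1.2 and in the KDPI entries of 7.4.2, so the mismatch is probably real. The 57-subject argument is fairly criticised: a 10% rate within the biopsy set gives a lower threshold, and k = 10 has no basis in the documents. What stands is that the cut-off can decide whether a model is fitted, not how likely that is.

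On BPAR, several caveats hold:

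- The mention of adverse events may be meant only as a list of data sources.
- The central-pathology sentence does not name BPAR. Applying it there is the natural reading, since BPAR is listed just before, but it is not explicit.
- SAP 5.5 refers to at least one central assessment, so one per participant rests on the submission rule in SAP 3.2.
- The SAP says that it clarified and adjusted the secondary objectives, so moving away from locally read BPAR may be deliberate.

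None of these reconciles the adverse-event wording with the protocol's biopsy requirement.

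**Conclusion.** The point holds and should be fixed. Item 10 as written has no inflammation criterion, and item 8 has two cut-offs that classify subjects scoring exactly 2 differently. BPAR is worded in SAP 6.1.2 in a way that conflicts with the protocol and leaves its source in the risk-factor models open.

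The numerical effect cannot be derived: the size of the biopsy set, the share scoring exactly 2, the joint distribution of i and ci, and the number of rejections reported only as adverse events are not in the documents. What the text fixes is a drop of k in the item 8 count and, on the literal count of 57, a band of k values in which the cut-off alone decides whether a model is run. Only secondary endpoints and analyses that use them are touched.

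**What to change.** Before database lock:

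1. Change item 10 in SAP 7.4.2 to IFTA and i above 0.
2. Align item 8 with the 6.1.2 definition (g+ptc of 2 or more). If above 2 was intended, correct 6.1.2 instead. Either way, leave one cut-off.
3. State in SAP 6.1.2 that a rejection reported as an adverse event counts as BPAR only when a local or central biopsy confirms it, and list the others separately.
4. Use that one definition in item 15, the four-part composite and the risk-factor models, and say in 7.4.2 whether the central-pathology sentence applies to BPAR. Name the data window and analysis set that go with it.

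The cost is SAP wording, plus matching rejection events to biopsy reports and one short listing. Central scores and local biopsy reports are already collected, so no new data are needed.

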15. BPAR

16. The four-part traditional composite endpoint

Separate risk factor analyses will be conducted for BID Immediate-release Tacrolimus treatment group only. Manufacturer will be included as additional covariate.

Ordinal assessments of antibody peak strength (weak, moderate, and strong) will be summarized based on the results over the course of one year using frequencies and percentages. Analysis of treatment group difference will be done using Fisher's Exact Test.

The continuous endpoint of Peak MFI score will be summarized with descriptive statistics based on the results over the course of one year by antibody.

Histopathology assessments will be summarized with both descriptive statistics and frequencies and percentages. Raw biopsy scores, including g, t, v, i, cg, ct, ci, cv, ah, ptc, and mm will be summarized as ordinal outcomes. Analysis of treatment group differences will be performed using Fisher's Exact Test. The incidence of binary outcomes including ci, ct, and ptc scores greater than 1 will be summarized with frequencies and percentages. Analysis of treatment group differences will be performed using Fisher's Exact test.

Assessments of association between De novo DSA and IA will be analyzed with logistic regression models using DSA formation as the response and IA as predictor using the same covariates detailed in Section 7.4.1.1.

Mean of eGFR by treatment group will be plotted across visits.

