The type of antibody reduction therapy will be summarized at each time point using frequencies and percentages. Analysis of treatment group differences will be conducted

using multinomial logistic regression and GEEs with the same covariates used in the primary endpoint's model and random effects(s), as necessary.

Ordinal assessments of antibody strength (weak, moderate, and strong) will be summarized at each time point using frequencies and percentages. Analysis of treatment group differences will be done by time point and overall using a proportional odds model and GEEs with the same covariates used in the primary endpoint's model and random effect(s), as necessary, to account for the temporal structure of data collection.

The continuous endpoint of MFI score will be summarized with descriptive statistics by time point. Due to the expected non-normality of errors, an analysis of treatment group differences will be implemented with a semi-parametric, mixed repeated measures model on rank scores using a random effect of subject and the same covariates included in the analysis of Section [7.4.1.1](#). Least square mean (LS Mean) estimates will be provided at each time point and treatment group differences will be assessed at each time point and overall.

Histopathology assessments will be summarized with both descriptive statistics and frequencies and percentages. Raw biopsy scores, including g, t, v, i, cg, ct, ci, cv, ah, ptc, and mm will be summarized as ordinal outcomes. Analysis of treatment group differences will be performed using the same proportional odds model and GEEs implemented for the analysis of antibody strength. The incidence of binary outcomes including ci, ct, and ptc scores greater than 1 will be summarized with frequencies and percentages. Analysis of treatment group differences will be done consistent with the models using GEEs for the other binary endpoints. For biopsy-based analyses, additional covariates will be added to the existing set in order to account for CIT, WIT, KDPI, DCD status, and the three ex vivo perfusion parameters recorded pre-transplant.

Assessments of association between DSA and IA will be analyzed overall and by treatment group with logistic regression models using DSA formation as the response and IA as predictor.

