3.3 Randomization

Randomization will be carried out using permuted blocks. The randomization allocation will consist of a 1:1 ratio for twice daily, immediate-release tacrolimus or Astagraf XL. The randomization will be stratified according to the following three factors:

- Planned use of alemtuzumab (Campath) (yes/no)
- Kidney donor profile index (KDPI) [three levels: N/A (living donors) vs. $\leq 50\%$ vs. $> 50\%$]
- HLA Class II mismatch (yes/no)

Additionally, enrollment of Campath users will be capped to not exceed 20% of the study population.

Subjects enrolled will be randomized using one central list via Interactive Response Technology (IRT). Prior to the initiation of the study treatment, the site staff will contact the IRT in order to determine the randomly assigned treatment. Specific procedures for randomization through the IRT are contained in the study procedures manual. Each subject

will be assigned a randomization number that is five digits long. The first two digits are chosen to be fixed for each strata; and the last three digits correspond to the sequential subject number (001 to 550) for the study subjects in each strata.

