4 SAMPLE SIZE

The sample size for this study was determined based upon a comparison of the rate of the two-part composite endpoint in the Astagraf XL group compared to the immediate-release tacrolimus group. Assuming a rate of 20% would be observed for the immediate-release tacrolimus group compared to a rate of 10% for the Astagraf XL group, 220 subjects per group are needed to achieve an 80% power to detect a difference between Astagraf XL and immediate-release tacrolimus with a two-sided alpha level of 0.05. The study will enroll 275 subjects/group (550 total) to allow for 20% dropout.

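### The SAP tests ordinal Banff scores and antibody strength with Fisher's exact test, which ignores category order, where the protocol had planned proportional-odds models; the change is not logged and costs power under a consistent shift.

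*SAP*

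**What the plan says.** SAP section 7.4.2 (Analysis of Secondary Endpoints) treats two groups of outcomes as ordinal.

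- **Antibody peak strength** (weak, moderate, strong): "Analysis of treatment group difference will be done using Fisher's Exact Test". SAP section 6.1.2 places this endpoint in the DSA-positive subset.
- **Eleven Banff scores**: "Raw biopsy scores, including g, t, v, i, cg, ct, ci, cv, ah, ptc, and mm will be summarized as ordinal outcomes", and these too are compared by Fisher's exact test. SAP sections 5.5 and 7.4 restrict central-pathology analyses to the Biopsy Analysis Set.

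Protocol section 7.4.2 planned a proportional-odds model with GEEs and the primary model's covariates for antibody strength. For the biopsy scores it said "Analysis of treatment group differences will be performed using the same proportional odds model and GEEs implemented for the analysis of antibody strength", with added donor and ischemia covariates.

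The SAP revision history (section 8) has nine entries, and none names this change of test. Entry 3 concerns overfitting in the risk factor analysis. Entry 7 concerns plasma exchange.

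**The concern.** On a table of ordered categories by two arms, Fisher's test treats the categories as labels. Exchanging weak with strong, or the lowest Banff score with the highest, leaves the p-value unchanged. The question is directional: the protocol's background section hypothesises that Astagraf XL reduces DSA and immune activation, so the natural question is whether scores are better or worse in one arm. Fisher's test does not answer that, and SAP 7.4.2 specifies no effect estimate to go with it for these outcomes.

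At stake is power in comparisons made only in subsets (biopsied patients, DSA-positive patients), together with the loss of a pre-specified ordinal effect measure.

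**Working it through.** **1. The plan's own figure.** The only design calculation (SAP section 4) is for the primary composite, at assumed event rates of 20% and 10% and a two-sided 5% level. It concludes that "220 subjects per group are needed to achieve an 80% power to detect a difference".

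- Without continuity correction, n = [1.960·√(2·0.15·0.85) + 0.842·√(0.20·0.80 + 0.10·0.90)]² / 0.10² = (0.990 + 0.421)² / 0.01 ≈ 199 per group.
- With continuity correction, n = (199/4)·[1 + √(1 + 4/(199·0.10))]² ≈ 219, which agrees with 220. Exact Fisher power at 220 per group is 81.1%.
- Dropout: 220 / 0.80 = 275.

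This reproduces, and it says nothing about the ordinal endpoints.

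**2. Inputs for the ordinal endpoints.** Neither document gives a category distribution, an effect size, the size of the Biopsy Analysis Set or the number of DSA-positive subjects. The following are therefore assumptions:

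- Banff scores: four levels (0-3), 30 to 200 per arm, odds ratio (OR) 1.3 to 3.
- Antibody strength: three levels, 10 to 50 per arm, OR 2 to 6.

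**3. Analytic approximation.** An unordered test on r levels has r − 1 degrees of freedom, while a test that uses the order has 1. A 1-df test at 5% has 80% power at noncentrality 7.85. At that same noncentrality:

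- 2 df (three levels): 70.9%, a loss of 80 − 70.9 = 9.1 points.
- 3 df (four levels): 64.5%, a loss of 80 − 64.5 = 15.5 points.

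**4. Simulation under a proportional-odds shift**, r × 2 Fisher test against tie-corrected Wilcoxon. Selected results:

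| Outcome, reference distribution | n/arm | OR | Fisher | Wilcoxon | Loss (points) |
|---|---|---|---|---|---|
| Banff .40/.30/.20/.10 | 60 | 2.5 | 57% | 75% | 18 |
| same | 100 | 2 | 59% | 75% | 16 |
| same* | 150 | 2 | 76.4% | 89.0% | 12.6 |
| Banff .80/.10/.06/.04* | 200 | 2 | 52.2% | 70.1% | 17.9 |
| Strength .40/.35/.25 | 50 | 3 | 71.5% | 80.3% | 8.8 |
| Strength .60/.30/.10 | 50 | 3 | 56.2% | 67.6% | 11.4 |
| same | 20 | 6 | 49.6% | 63.9% | 14.3 |
| Strength .80/.15/.05 | 50 | 6 | 61.3% | 73.1% | 11.8 |

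*Fisher side from the 3-df chi-square approximation.

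Across the scenarios with rank-test power of 60-90%, the loss is about 12 to 19 points for Banff scores and 9 to 15 for antibody strength. Outside that band it runs from about 1 to 21.

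**5. Where the loss is small.** With a mostly-zero score (.90/.06/.03/.01) and OR 1.8, power is 19% vs 26% at 100 per arm and 11% vs 13% at 50 per arm. For antibody strength (.60/.30/.10) at 15 per arm and OR 2, it is 9.5% vs 14.7%. Both tests are weak in these settings. At large odds ratios the gap widens even in small subsets: 18.2% vs 33.0% at 10 per arm and OR 6.

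**6. A caution on the smallest subsets.** With no effect and 10 to 20 per arm, under the two more skewed strength distributions, Fisher rejected in 1.1-4.0% of runs and the tie-corrected Wilcoxon in 3.7-5.4%. Part of the gap there is the conservatism of an exact test, which an exact Wilcoxon would share. The upper end of the antibody-strength range is therefore optimistic for the exact version.

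**7. Where the comparison reverses.** For a non-monotone difference (.40/.30/.20/.10 vs .50/.10/.20/.20, 60 per arm), Fisher has 72% power and Wilcoxon 5%.

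**The case against.** The strongest reply has four parts.

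- **Validity and weight.** Fisher's test holds its error rate. These are secondary comparisons without planned power or multiplicity adjustment, in a study that calls itself exploratory. SAP section 3.1.2 now says antibody strength is to be summarised and histopathology examined. The defined histology endpoints (TG, microcirculatory inflammation, IFTA, ABMR, BPAR) are compared by covariate-adjusted logistic regression, subject to the event-rate rule in SAP 7.1. All of this stands and limits the importance of the point, although SAP 7.4.2 still tests the ordinal outcomes.
- **No trial inputs.** Every distribution, odds ratio and subset size above is assumed. This stands too. At the planning rates, 0.20 × 220 = 44 and 0.10 × 220 = 22 subjects would have the composite event, and DSA-positives are only some of these. The interim decision in SAP 7.9 suggests a control rate that was not low, but gives no DSA count. With 15-20 positives per arm and OR 2.5, power is 17-23% vs 21-30%, a loss of about 4-7 points. With fewer than 15 in a group, the descriptive-only rule for analysis sets in SAP 7.1 may mean that no test is run.
- **Sparse data explains the move.** SAP 3.1.2 cites data availability, and SAP 7.1 bars regression models for outcomes with under 10% events. That is a plausible reason to leave the GEE models. It is not a reason to discard the order: an exact Wilcoxon test is equally valid in sparse tables and is not a regression model.
- **The remedy is not the protocol's model.** Correct: an unadjusted Wilcoxon drops the covariates, as Fisher's does, and its p-value alone is not an effect size. The estimate has to be requested separately.

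A reader might go further and infer that the trial gives up one fixed amount of power, such as 15 points, on all these comparisons. The documents do not support that: 15.5 points belongs to a four-level score at 80% ordered-test power, and the three-level figure at that power is 9.1. A reader might also infer that Fisher's test is wrong here or that the main result is weakened. Neither follows.

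**Conclusion.** The point holds as a matter of efficiency and consistency. The SAP calls these outcomes ordinal, tests them with a method that ignores order, and departs from the protocol's ordinal models without logging or explaining it. The estimated cost (12-19 points for four-level scores, 9-15 for three-level strength, at 60-90% rank-test power) rests on a proportional-odds shift and on assumed levels, distributions, odds ratios and numbers per arm. A consistent shift is the protocol's own modelling assumption for these outcomes. For mostly-zero scores or very small subsets at modest effects, both tests have little power and the choice between them matters by only a few points. The change is worth making because it is nearly free.

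**What to change.** In SAP 7.4.2:

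- Compare the eleven Banff scores and antibody peak strength by an exact Wilcoxon rank-sum (row-mean-score) test, or by the protocol's proportional-odds model where data allow.
- Report a common odds ratio, or the probability that one arm scores higher, with a 95% CI.
- Keep Fisher's exact test for the binary ci, ct and ptc outcomes (score above 1).
- Record the departure from the protocol, with its reason, in the revision history.

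The cost is a few lines of text and a different procedure option, with no new data. The downside is that a rank test has little power against a non-monotone difference. The frequency tables already planned would still show one.
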